## 1. VERSION HISTORY

**Table 1. Summary of Changes** 

Version/ Date	Associated Protocol Amendment	Rationale	Specific Changes	
1 13 Mar 2023	Original 31 Jan 2023	N/A	N/A	
2 25 Sep 2023	Original 31 Jan 2023	1. Updated the Phase 1 safety analysis based on FDA feedback on multiple programs	1. Section 3.1.2, Section 5.3.1.1, Section 6.1.2, Section 6.1.4.3	
		2. Added details of the Phase 2/3 safety analysis based on the new e-diary and CRF	2. Section 3.1.3, Section 6.1.3, Section 6.1.5	
		3. Added information on AESIs	3. Section 3.1.2.3, Section 3.1.3.2	
		4. Added the Tier 1 analysis per FDA BLA review comments (Phase 2/3)	4. Section 3.5.2, Section 6.6.1	
		5. Clarified the Phase 1 immunogenicity analysis	5. Section 2.2.3	
		6. Added additional clarification on analysis	6. Section 6.5.2	
3 06 Mar 2024	Protocol amendment 1 09 Feb 2024	1. Removed the Phase 2/3 content	1. Throughout the SAP	
	071002024	2. Updated the AESI terms per new CRF	2. Section 3.1.1.3	
		3. Updated the other endpoints with seroresponse	3. Section 3.3.1, Section 6.3	
		4. One reference was removed (Miettinen O, Nurminen M)	4. Section 8	

#### 2. INTRODUCTION

This SAP provides the detailed methodology for summary and statistical analyses of the data collected in Study C3671016.

This document may modify the plans outlined in the protocol; however, any major modifications of the primary endpoint definition or its analysis will also be reflected in a protocol amendment.

## 2.1. Modifications to the Analysis Plan Described in the Protocol

There is no change in analysis from the plan specified in the protocol.

## 2.2. Study Objectives, Endpoints, and Estimands

Type	Objective	Endpoint	Estimand
Primary Safety	To describe the safety and tolerability of RSVpreF at each dose level in children 5 to <18 years of age and children 2 to <5 years of age.	Local reactions (pain at the injection site, redness, and swelling). Systemic events (fever, vomiting, diarrhea, headache, fatigue/tiredness, muscle pain, and joint pain). AEs. SAEs. NDCMCs.	
 
In participants receiving 1 dose of study intervention at each dose level, for each age stratum:
 
The percentage of participants reporting local reactions within 7 days after vaccination.
 
The percentage of participants reporting systemic events within 7 days after vaccination.
 
The percentage of participants reporting AEs from vaccination through 1 month after vaccination.
 
The percentage of participants reporting SAEs throughout the study.
 
The percentage of participants reporting NDCMCs throughout the study.
 

Secondary Immunogenicity	To describe the immune responses elicited by RSVpreF at each dose level in children 5 to <18 years of age and children 2 to <5 years of age.	RSV A and RSV B NTs.	In participants in compliance with the key protocol criteria (evaluable immunogenicity population):  GMTs of NT for RSV A and RSV B 1 month after vaccination.  GMTs of NT for RSV A and RSV B before vaccination.  GMFRs of NT for RSV A and RSV B from before vaccination to 1 month after vaccination.

Туре	Objective	Endpoint	Estimand
Secondary Immunogenicity	To describe the cell-mediated immune response in children 5 to <18 years of age and children 2 to <5 years of age.	RSV F antigen–specific CD4+ T cells secreting IFNy. RSV F antigen–specific CD4+ T cells secreting IL-4.	
 
In participants in compliance with the key protocol criteria (evaluable immunogenicity population):
 
Median frequencies of RSV F antigen–specific CD4+ T cells expressing IFNγ before vaccination and 1 month after vaccination.
 
Median frequencies of RSV F antigen–specific CD4+ T cells expressing IL-4 before vaccination and 1 month after vaccination.
 

## 2.2.1. Primary Estimand(s)

#### 2.2.1.1. Primary Safety Estimands

## 2.2.1.1.1. Reactogenicity Estimands

Reactogenicity estimands have the following 5 attributes:

- Treatment condition: Up to 2 dose levels received on Day 1 from each cohort are applicable for safety estimands. Therefore, up to 6 dose/age groups are applicable to treatment condition: 1) RSVpreF 120 μg in the 5- to <18-year-old healthy cohort; 2) RSVpreF 120 μg in the 5- to <18-year-old cohort with chronic medical conditions; 3) RSVpreF 120 μg in the 2- to <5-year-old cohort; 4) RSVpreF 60 μg in the 5- to <18-year-old cohort with chronic medical conditions; and 6) RSVpreF 60 μg in the 2- to <5-year-old cohort.
- **Population:** Pediatric participants as defined by the study inclusion/exclusion criteria in the Phase 1 cohort.
- Variables: Each item included in the e-diary from Days 1 through 7 after vaccination for each treatment condition (refer to Section 3.1.1.1 and Section 3.1.1.2).
- Intercurrent events: All data collected after the intercurrent event will be included.
- Population-level summary: The rates of the variables (reporting each reactogenicity item) in each treatment condition (by dose/age/risk) separately.

## 2.2.1.1.2. **AE Estimands**

AE estimands have the same attributes (treatment condition, population, intercurrent events, population-level summary) as reactogenicity estimands (Section 2.2.1.1.1), except:

• Variables: AEs reported within 1 month after vaccination (Section 3.1.1.3).

#### **2.2.1.1.3. SAE Estimands**

SAE estimands have the same attributes (treatment condition, population, intercurrent events, population-level summary) as reactogenicity estimands (Section 2.2.1.1.1), except:

• Variables: SAEs reported throughout the study (Section 3.1.1.3).

## 2.2.1.1.4. NDCMC Estimands

NDCMC estimands have the same attributes (treatment condition, population, intercurrent events, population-level summary) as reactogenicity estimands (Section 2.2.1.1.1), except:

• Variables: NDCMCs reported throughout the study (Section 3.1.1.3).

## 2.2.2. Secondary Estimand(s)

All secondary estimands for immunogenicity objectives will use the hypothetical strategy and describe the RSVpreF immune response in participants without the intercurrent events. In other words, the immune response is estimated in the hypothetical setting where participants follow the study schedule and protocol requirements as directed. Each is defined in the subsections below.

## 2.2.2.1. Secondary Immunogenicity Estimands

#### 2.2.2.1.1. Secondary RSV NT Immunogenicity Estimands

- Treatment condition: Up to 6 dose/age groups received on Day 1 from the study cohort are applicable to treatment condition: 1) RSVpreF 120 μg in the 5- to <18-year-old healthy cohort; 2) RSVpreF 120 μg in the 5- to <18-year-old high-risk cohort; 3) RSVpreF 120 μg in the 2- to <5-year-old cohort; 4) RSVpreF 60 μg in the 5- to <18-year-old healthy cohort; 5) RSVpreF 60 μg in the 5- to <18-year-old high-risk cohort; and 6) RSVpreF 60 μg in the 2- to <5-year-old cohort.
- **Population:** Pediatric participants as defined by the study inclusion/exclusion criteria for the Phase 1 cohort.
- Variables: RSV serum NTs for subgroup A and subgroup B.
- Intercurrent events: The following intercurrent events could impact the interpretation or the measurement of the immune response:
  - 1. The participant did not receive RSVpreF as randomized in each study.
  - 2. The participant did not meet the study inclusion criteria or did meet the exclusion criteria.
  - 3. Major protocol violations: The participant received a prohibited vaccine or treatment that may alter the immune response.

4. Blood was taken outside an acceptable window for immunogenicity evaluation (<27 days or >42 days after RSVpreF).

The clinical question of interest is based on the comparison the immune response elicited from RSVpreF in pediatric participants from this study's cohort, without any influence from any other immune-modifying drugs or vaccines and measured within a homogeneous time window. Therefore, all data after intercurrent events 1, 2, and 3, as well as all data at intercurrent event 4, if collected, will be excluded. Major protocol violations will be determined by clinical review.

• **Population-level summary**: GMT of NT before vaccination and 1 month after vaccination, and GMFR of NT from before vaccination to 1 month after vaccination, in each treatment condition (by age/with or without chronic medical condition group/dose level) separately.

## 2.2.2.1.2. Secondary PBMC Immunogenicity Estimands

PBMC immunogenicity estimands have the same attributes (treatment condition, population, and intercurrent events) as RSV immunogenicity estimands (Section 2.2.2.1.1), except:

- Variables: RSV F antigen–specific CD4+ T cells secreting IFNγ and IL-4.
- Population-level summary: Median frequency before vaccination and 1 month after vaccination, in each treatment condition (by age/risk group) separately.

## 2.2.3. Additional Estimand(s)

Additional estimands, as supplemental analyses to support the primary and secondary immunogenicity objectives, are defined. The table below lists the strategies for addressing intercurrent events, which are listed in Section 2.2.1 and Section 2.2.2 for the immunogenicity objectives. The remaining estimand attributes are the same for each objective.

Immunogenicity Objective	Intercurrent Event Handling Strategy
Secondary RSV NT immunogenicity	Treatment policy
Secondary PBMC immunogenicity	Treatment policy

For the immunogenicity objectives, the treatment policy will be based on actual age, risk condition, and the vaccine received, as the 6 groups are not randomized.

## 2.3. Study Design

This is a Phase 1 open-label, age-descending, dose-finding study of the safety, tolerability, and immunogenicity of RSVpreF in RSV-seropositive children 2 to <18 years of age. Up to 120 participants will receive RSVpreF with up to 2 dose levels across 2 age strata (2 to <5 years and 5 to <18 years) and 2 risk substrata in the older group (5 to <18 years of age). Approximately 60 to 120 participants are expected to be enrolled.

Age Stratum (Years)	Number of Participants
2 to <5	~20/~20ª
5 to <18	~40/~40 a,b
Total	~60-120

- a. Up to 2 dose levels of RSVpreF (120  $\mu$ g and 60  $\mu$ g) will be tested in participants.
- b. Approximately 40 participants 5 to <18 years old will be enrolled, with ~20 healthy participants and ~20 participants with high-risk chronic medical conditions receiving each dose level.

For all participants enrolled, local reactions (redness, swelling, and pain at the injection site) and systemic events (fever, vomiting, diarrhea, headache, fatigue/tiredness, muscle pain, and joint pain) are collected from Day 1 (vaccination day) through Day 7 via the e-diary. AEs are collected from consent through the 1-month postvaccination visit. Additionally, AEs occurring up to 48 hours after blood draws that are related to study procedures are reported in the CRF. SAEs and NDCMCs will be collected from the time the participant's parent(s)/legal guardian provide informed consent through the duration of the study.

All participants 2 to <5 years of age must be seropositive. RSV serostatus will be determined before vaccination. Blood samples are collected before vaccination and at the 1-month postvaccination visit to assess RSV A and RSV B NT, as well as cell-mediated immune response through measuring RSV F antigen–specific CD4+ T cells secreting IFNγ and RSV F antigen–specific CD4+ T cells secreting IL-4.

# 3. ENDPOINTS AND BASELINE VARIABLES: DEFINITIONS AND CONVENTIONS

## 3.1. Primary Endpoint(s)

#### 3.1.1. Primary Safety Endpoints

Primary safety endpoints include both reactogenicity data collected from the e-diary and AE data collected from the CRF.

Based on feedback from the FDA on multiple vaccine programs, reactogenicity data will utilize both e-diary data (prompted local reactions and systemic events) and reactogenicity events (related or unrelated) reported in the AE CRF during the e-diary collection period. Since the AE CRF does not designate a specific page to collect reactogenicity data for an untransmitted e-diary, Pfizer has adopted a process of providing a listing of AEs reported within 7 days after vaccination to the clinical team to review and determine ("flag") which

PTs should be considered reactogenicity events before the database lock. AEs reported on the same day of vaccination but missing a start time are defaulted to AEs reported after vaccination. Following these review steps, those AEs reported within 7 days after vaccination that match flagged PTs (either related or unrelated) will be considered reactogenicity data. If the same reactogenicity event is reported on the same day from both the e-diary and the AE CRF, the highest grade from the 2 data sources will be used for that specific day for analysis.

It should be noted that the data collection in the AE CRF is different from that of the e-diary:

- For redness, swelling, and fever, the measured size of redness and swelling at the injection site and temperature are recorded in the e-diary, but not in the AE CRF. As the missing e-diary entries are monitored with ongoing review of the prompted reactions reported in the AE CRF, any measurement recorded in the query response will be taken into consideration for the primary analysis using the data handling memo for analysis purposes. For the 7 days, only the maximum grading from both sources will be used for the aggregated severity analysis.
- For pain at the injection site and all other systemic events, the severity grading algorithm for the e-diary data and the AE CRF may not be the same. Pfizer will choose the highest-severity grade.

If a participant did not have any e-diary data transferred within 7 days after vaccination, the AE CRF data will not be used for derivation, because doing so may inflate the denominator and bias the analysis, since participants who did not transfer e-diary data may be less likely to report reactogenicity data. If a participant did not report any e-diary data, the participant will not be included in the analysis of reactogenicity data.

The subsections below describe how to derive each safety endpoint.

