8.3.4.2. Local Reactions

During the reactogenicity e-diary reporting period, participants or participants' parents/legal guardians will be asked to assess redness, swelling, and pain at the injection site and to record the symptoms in the reactogenicity e-diary daily for 7 days (Days 1 through 7) after each vaccination. If a local reaction persists beyond the end of the reactogenicity e-diary period following vaccination, the participant or participant's parent(s)/legal guardian will be requested to report that information. The investigator will enter this additional information in the CRF.

Participants will be provided with a measuring device. Redness and swelling will be measured and recorded in caliper units (measuring device units; range: 1 to 14 caliper units for participants \geq 2 to <12 years of age and 1 to 21 caliper units for participants \geq 12 to 18 years of age) for the first 7 days following vaccination (Days 1 through 7), and then categorized as absent, mild, moderate, or severe using the scale shown in Table 2. Measuring device units can be converted to centimeters according to the following formula: 1 measuring device unit = 0.5 cm. Pain at the injection site will be assessed by the participants or participants' parent(s)/legal guardians as absent, mild, moderate, or severe according to the grading scale in Table 2.

If a Grade 3 local reaction is reported in the reactogenicity e-diary (redness or swelling >14 caliper units for participants <12 years of age or >20 caliper units for participants ≥12 years of age; Grade 3 pain at the injection site), a telephone contact should occur to ascertain further details and determine whether a site visit is clinically indicated. Only an investigator or medically qualified person is able to classify a participant's local reaction as Grade 4. If a participant experiences a confirmed Grade 4 local reaction, the investigator must immediately notify the sponsor and, if it is determined to be related to the administration of the study intervention, further vaccinations (if applicable) will be discontinued in that participant.

1 40010 21	Event Henricon Graning Senie				
	Participant Age	Mild (Grade 1)	Moderate (Grade 2)	Severe ^a (Grade 3)	Potentially Life-Threatening ^b (Grade 4)
Pain at the injection site	≥2 Years	Does not interfere with activity	Interferes with activity	Prevents daily activity	Emergency room visit or hospitalization for severe pain at the injection site

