9.3.2. Primary Endpoint(s)/Estimand(s) Analysis

Table 5. Primary Endpoint Analyses

Endpoint	Statistical Analysis Methods
Safety	 Descriptive statistics will be provided for each reactogenicity endpoint for each RSVpreF dose level within each age stratum. Local reactions (redness, swelling, and pain at the injection site) and systemic events (fever, fatigue/tiredness, headache, vomiting, diarrhea, muscle pain, and joint pain) from Day 1 through Day 7 after vaccination will be presented by maximum severity and any severity. Descriptive summary statistics will include counts and percentages of participants with the indicated endpoint and the associated Clopper-Pearson 95% CI (Section 9.3.1.1). AEs and SAEs will be categorized according to MedDRA terms. All of the AEs within 1 month and SAEs/NDCMCs throughout the study will be descriptively summarized with counts, percentages, and associated Clopper-Pearson 95% CIs for each RSVpreF dose level within each age stratum (Section 9.3.1.1). Descriptive summaries may also be provided for the combined age group (2 to <18 years) within the same RSVpreF dose level.

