- When an AE or SAE occurs, it is the responsibility of the investigator to review all documentation (eg, hospital progress notes, laboratory reports, and diagnostic reports) related to the event.
- The investigator will then record all relevant AE or SAE information in the CRF.
- It is **not** acceptable for the investigator to send photocopies of the participant's medical records to Pfizer Safety in lieu of completion of the Vaccine SAE Reporting Form/AE or SAE CRF page.
- There may be instances when copies of medical records for certain cases are requested by Pfizer Safety. In this case, all participant identifiers, with the exception of the participant number, will be redacted on the copies of the medical records before submission to Pfizer Safety.

• The investigator will attempt to establish a diagnosis of the event based on signs, symptoms, and/or other clinical information. Whenever possible, the diagnosis (not the individual signs/symptoms) will be documented as the AE or SAE.

Assessment of Intensity

The investigator will make an assessment of intensity for each AE and SAE reported during the study and assign it to 1 of the following categories:

GRADE	If required on the AE page of the CRF, the investigator will use the adjectives MILD, MODERATE, SEVERE, or LIFE-THREATENING to describe the maximum intensity of the AE. For purposes of consistency, these intensity grades are defined as follows:	
1	MILD	Does not interfere with participant's usual function.
2	MODERATE	Interferes to some extent with participant's usual function.
3	SEVERE	Interferes significantly with participant's usual function.
4	LIFE-THREATENING	Life-threatening consequences; urgent intervention indicated.

An event is defined as "serious" when it meets at least 1 of the predefined outcomes as described in the definition of an SAE, NOT when it is rated as severe.

Assessment of Causality

- The investigator is obligated to assess the relationship between study intervention and each occurrence of each AE or SAE. The investigator will use clinical judgment to determine the relationship.
- A "reasonable possibility" of a relationship conveys that there are facts, evidence, and/or arguments to suggest a causal relationship, rather than a relationship cannot be ruled out.

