## 3.1.1.1.2. Maximum Severity of Local Reactions Within 7 Days After Vaccination

The grading of local reactions is listed in Table 4.

**Table 4.** Grading Scale for Local Reactions

	Mild Grade 1	Moderate Grade 2	Severe Grade 3	Grade 4 a
Redness	Mild grading from the e-diary per Table 2 in the protocol or mild from the AE CRF	Moderate grading from the e-diary per Table 2 in the protocol or moderate from the AE CRF	Severe grading from the e-diary per Table 2 in the protocol or severe from the AE CRF	Necrosis or exfoliative dermatitis
Swelling	Mild grading from the e-diary per Table 2 in the protocol or mild from the AE CRF	Moderate grading from the e-diary per Table 2 in the protocol or moderate from the AE CRF	Severe grading from the e-diary per Table 2 in the protocol or severe from the AE CRF	Necrosis

	Mild Grade 1	Moderate Grade 2	Severe Grade 3	Grade 4ª
Pain (at the injection site)	Does not interfere with activity (mild from the e-diary or AE CRF)	Interferes with activity (moderate from the e-diary or AE CRF)		Emergency room visit or hospitalization for severe pain at the injection site

**Table 4.** Grading Scale for Local Reactions

The following variables are derived for each participant:

1. Maximum severity of each local reaction on any day (Day 1 through Day 7).

The maximum severity (highest grading) of each local reaction within 7 days after vaccination will be derived. The maximum severity will be derived as follows:

- = Missing, if values are missing for all days (Days 1-7);
- = 0, if the participant reports all reactions as "no" or a combination of missing and "no" for all days (Days 1-7);
- = Highest grade (maximum severity either from the e-diary or in the AE CRF) within 7 days after vaccination if the answer is not "no" for at least 1 day.
- 2. Maximum severity of any local reaction on any day (Day 1 through Day 7).

The maximum severity for any local reaction will be derived as follows:

- = Missing, if values are missing for all days (Days 1-7) across all 3 local reactions;
- = 0, if the participant reports all reactions as "no" or a combination of missing and "no" for all days (Days 1-7) for all individual local reactions;
- = *Highest grade* (maximum severity) within 7 days after vaccination, if the answer is not "no" for at least 1 day for at least 1 local reaction.

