## 3.1.1.2. Systemic Events Within 7 Days After Vaccination

Systemic events, including fever, fatigue/tiredness, headache, vomiting, diarrhea, muscle pain, and joint pain, are reported from Day 1 through Day 7 after vaccination, where Day 1 is the day of vaccination with RSVpreF or placebo. The derivations for the systemic events as described below will be handled similarly to the way that local reactions are handled for the presence for each participant, severity level, duration, onset day, and presence of systemic event on each and any day.

- 1. Presence (yes or no) of each systemic event on any day (Day 1 through Day 7) after vaccination.
- 2. Presence (yes or no) of any systemic event on any day (Day 1 through Day 7) after vaccination.

- 3. Maximum severity of each systemic event on any day (Day 1 through Day 7) after vaccination.
- 4. Maximum severity of any systemic event on any day (Day 1 through Day 7) after vaccination.
- 5. Duration of each systemic event after vaccination.
- 6. Onset day of each systemic event after vaccination.
- 7. Presence (yes or no) of each systemic event on each and any of the 7 days after vaccination.
- 8. Presence (yes or no) of any systemic event on each and any of the 7 days after vaccination.

The grading scale for systemic events is provided in the protocol. However, the derivation of severity of each systemic event on each day should be based on the maximum severity reported from the e-diary or AE CRF, if data are reported from both sources; or the e-diary alone if not reported from the AE CRF.

Fever is defined as a temperature of  $\geq 100.4^{\circ}\text{F}$  ( $\geq 38.0^{\circ}\text{C}$ ). The highest temperature for each day will be recorded in the e-diary. For reporting purposes, fever will be analyzed using the following temperature ranges:

- Mild ( $\geq$ 38.0 to 38.4°C from the e-diary or mild grade from the AE CRF);
- Moderate (>38.4 to 38.9°C from the e-diary or moderate grade from the AE CRF);
- Severe (>38.9 to 40.0°C from the e-diary or severe grade from the AE CRF);
- Grade 4 (>40.0°C from the e-diary or severe grade from the AE CRF, plus documented >40.0°C via CRF query or other sources).

If a participant reports a fever (or severity of fever) by accident, the correct temperature will be transcribed in a data handling memo to be included in the analysis, and the temperature that is confirmed as incorrect will not be included in the analysis.

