#### 6.1.2.1. Main Analysis

- Estimand strategy: Treatment policy (Section 2.2.1.1.2).
- Intercurrent events and missing data: All data collected are included.
- Analysis set: Safety population (Section 4).
- Analysis timing: At primary analyses (when all primary endpoint data are available).
- Analysis methodology: 95% CIs of the proportion of participants reporting those events will use the Clopper-Pearson method (Section 5.2.1).
- Descriptive statistics, including the proportion (%), the numerator (n) and the denominator (N) used in the proportion calculation, and the 95% CI for percentage using the Clopper-Pearson method, will be presented for each vaccine group for each analysis interval (Section 5.2.1).
- Bar charts with the proportions of participants for each variable within the specified interval will be plotted for each group. The bars may be divided into relatedness categories to highlight the proportions of participants with related events.
- The main analysis will be based on AEs and will exclude the reactogenicity events that were reported in the AE CRF (except for SAEs) (Section 3.1.1.3).

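### Does combining a daily e-diary grade with a whole-event AE-CRF grade distort the 7-day maximum severity tables?

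*SAP*

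**What the plan says.** SAP Section 3.1.1 builds the reactogenicity data from two sources: the e-diary, and "those AEs reported within 7 days after vaccination that match flagged PTs". Where both report the same event on the same day, "the highest grade from the 2 data sources will be used for that specific day for analysis". For the 7-day severity summary it takes the maximum over both sources. Table 4 (SAP Section 3.1.1.1.2) and SAP Section 3.1.1.2 carry this into the grades; the severe fever category, for example, begins "Severe (>38.9 to 40.0°C from the e-diary or severe grade from the AE CRF".

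The two grades are of different kinds. In Protocol Section 8.3.4.2, redness and swelling are measured daily in caliper units "and then categorized as absent, mild, moderate, or severe using the scale shown in Table 2", and Section 8.3.4.4 grades fever by temperature. Protocol Section 10.2.3 has the investigator grade an AE "to describe the maximum intensity of the AE", on a scale of interference with usual function.

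Protocol Section 9.3.1 and SAP Section 5.3.1.1 describe AE-CRF data as filling in partly missed diary days. SAP Section 2.1 declares no departure from the protocol. In Protocol Table 5, local reactions and systemic events over Days 1 to 7 "will be presented by maximum severity and any severity". SAP Section 6.1.1.3 repeats the maximum-severity analysis on e-diary data alone and presents the difference.

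**The concern.** A rule worded for a single day is given a grade that belongs to a whole event. The SAP does not say whether that grade applies to the start day, to every day from start to stop, or only to days on which the diary also records the event. Nor does it say what happens if the event peaks after the window closes. Suppose a child's diary shows 38.1°C on Day 7, and a fever AE starting that day becomes severe on Day 9. The child could then be counted as severe within 7 days.

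The second worry is transparency. The protocol grades redness, swelling and fever by measurement and mentions CRF data only for missed days. The SAP lets a CRF grade exceed a valid measurement, yet declares no change. Maximum severity is part of the primary safety output and groups are small, so a single regraded child is visible when dose levels are compared.

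**Working it through.** **1. Does day coverage change the main output?** Let e(d) be the diary grade on day d and g the CRF grade, applied to some set of days within Days 1 to 7. The 7-day maximum is

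max over d of max(e(d), c(d)), with c(d) = g on the covered days and 0 elsewhere.

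For any non-empty set of covered days this equals max(max e(d), g). The choice of days drops out.

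Illustration (assumed data): the diary is sent on all 7 days with grades 1, 1, 1, 0, 0, 0, 0. One CRF event runs from Day 2 to Day 10 with maximum grade 3.

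| Reading of the CRF grade | Days 1 to 7 | 7-day maximum | Days present | Days at grade 3 |
|---|---|---|---|---|
| E-diary only | 1,1,1,0,0,0,0 | 1 | 3 | 0 |
| Start day only | 1,3,1,0,0,0,0 | 3 | 3 | 1 |
| Every day from start to stop | 1,3,3,3,3,3,3 | 3 | 7 | 6 |
| Only days also positive in the diary | 1,3,3,0,0,0,0 | 3 | 3 | 2 |

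All three ways of using the CRF grade give a maximum of 3. What varies is presence by day (3 or 7 days). That is a supplementary summary without confidence intervals (SAP Section 6.1.1.2), and no daily severity table is planned.

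**2. What remains?** Only a peak after Day 7. It requires a flagged AE that starts by Day 7, a CRF entry alongside the diary, and a later peak above every grade reached in the window. Protocol Section 8.3.4 says diary events need not be entered as AEs. Events still ongoing when the diary ends are followed for stop dates. Severe reactions seen at an unscheduled visit have their own CRF page (Protocol Section 8.11). Double entry can still happen: acute reactions in the first 30 minutes go on the AE page. It is not the normal route for a reaction still building on Day 7.

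**3. How large could it be?** The documents give no frequency, so 0, 1 or 2 affected children are assumed. Clopper-Pearson limits for x of n are the 2.5% quantile of Beta(x, n−x+1) and the 97.5% quantile of Beta(x+1, n−x), with a lower limit of 0 when x = 0.

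| Affected | n about 20 (age/risk/dose group) | n about 40 (older stratum, one dose) |
|---|---|---|
| 0 | 0% (0 to 16.8) | 0% (0 to 8.8) |
| 1 | 5.0% (0.1 to 24.9) | 2.5% (0.1 to 13.2) |
| 2 | 10.0% (1.2 to 31.7) | 5.0% (0.6 to 16.9) |

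One child is 1/20 = 5.0 points or 1/40 = 2.5 points, always upward. These intervals would fit any one-child issue and do not show that the event occurs.

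**4. Would altering the rule help?**
- Spreading the CRF grade over every day from start to stop leaves the post-Day-7 peak in the maximum. It also turns four diary-recorded absences (Days 4 to 7 above) into grade 3.
- Letting the measurement override the CRF would lower the primary grade. SAP Sections 3.1.1.3 and 6.1.2.1 remove flagged non-serious reactogenicity from the main AE analysis, so the higher grade would survive only in the Section 6.1.2.3 sensitivity analysis.
- Footnote counts of AEs lasting past Day 7 cannot date the peak when the CRF holds one grade per event.

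**The case for a change.** The strongest case for acting is that the remedy is cheap and the output is primary. The internal review committee weighs safety and tolerability when it selects a dose, and SAP Section 2.1 is the place where a reader looks for departures from the protocol. The e-diary-only comparison is also a blunt instrument. It pools measured days regraded by the CRF, which the protocol does not describe, with missed days filled from the CRF, which it does. In a group of 20, one child of either kind gives the same 5.0-point difference.

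Much of this is true as description. Day coverage is unstated, Section 2.1 omits the same-day rule, and the planned difference does not separate its two sources. Less stands as a reason for change. Protocol Section 9 expects the SAP to add detail and allows it to modify the analysis, reserving a protocol amendment for major changes to primary endpoints or their analyses. The same-day rule is a grading detail on which Protocol Section 9.3.1 is silent. Where the diary already records the event, it leaves the primary estimand, the percentage of participants reporting it, untouched. The rule appears in three places in the SAP, and Section 3.1.1 attributes the approach to FDA feedback. The committee's reviews of data up to 7 days draw on e-diary and AE data (Protocol Section 4.1.2), and stopping rules 3 and 4 do not use this derived grade. Because the two sources are collected separately, a particular child's grade can be traced if it matters.

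**Conclusion.** No change is needed. The missing day coverage is a gap that an analyst can fill sensibly: the CRF grade of a flagged event enters the 7-day maximum, and the choice of days within the window cannot alter that figure. Taking the higher of two sources is a fair trade-off. It may occasionally overstate severity, and in return a clinician's higher grade stays in the main tables. A line in SAP Section 2.1 would be tidier, but it would change no number.

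The residual effect is a possible upward shift of 5.0 points per child in a group of about 20, or 2.5 points in about 40, in descriptive tables with no hypothesis. This rests on three assumptions: the AE page holds one undated grade per event (the CRF itself is not among the documents); late-peaking, doubly reported events are uncommon, for which the documents give no figure; and the e-diary-only analysis in SAP Section 6.1.1.3 is reported with its difference as planned.
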